### LIST OF ABBREVIATIONS AND DEFINITION OF TERMS

Abbreviation	Term			
AE	Adverse Event			
AMD	Age-Related Macular Degeneration			
ANCOVA	Analysis of Covariance			
ATC	Anatomic Therapeutic Chemical			
BCVA	Best Corrected Visual Acuity			
BUN	Blood Urea Nitrogen			
CI	Confidence Interval			
CNV	Choroidal Neovascularization			
ECG	Electrocardiogram			
ECOG	Eastern Cooperative Oncology Group			
ETDRS	Early Treatment Diabetic Retinopathy Study			
FA	Fluorescein Angiography			
FAF	Fundus Autofluorescence			
FP	Fundus Photography			
GA	Geographic Atrophy			
GEE	Generalized Estimating Equations			
GGT	Gamma-glutamyl Transferase			
ICH	International Conference on Harmonization			
IOP	Intraocular Pressure			
ITT	Intention-to-Treat			
LLN	Lower Limit Normal			
LOCF	Last Observation Carried Forward			
MAR	Missing at Random			
MCAR	Missing Completely At Random			
MedDRA	Medical Dictionary for Regulatory Activities			
MI	Multiple Imputation			
MRM	Model for Repeated Measures			
NA	Not Available / Not Applicable			
OU	Oculus Uterque (Both Eyes)			
РК	Pharmacokinetic			
PP	Per-Protocol			
PSC	Posterior Subcapsular Cataract			
REML	Restricted Maximum Likelihood			
SAE	Serious Adverse Event			
SAP	Statistical Analysis Plan			

SD	Standard Deviation
SE	Study Eye
SGOT/AST	Aspartate Aminotransferase
SGPT/ALT	Alanine Aminotransferase
ULN	Upper Limit Normal
VA	Visual Acuity
WBC	White Blood Cells
WHO	World Health Organization
WOCF	Worst Observation Carried Forward

### **1 INTRODUCTION**

This Statistical Analysis Plan describes the statistical methodology and data handling for the clinical trial with Protocol Number: OPH2003 and Version Date: 28 March 2018.

The trial consists of a total treatment period of 18 months. This SAP covers all analyses to be performed on the 1 year data. By pre-specification, a screening analysis will be performed to assess whether the effect of Zimura on the rate of Geographic Atrophy (GA) growth is plausibly more efficacious (or reliably more efficacious) than that of the sham control on the rate of GA growth over 12 months. Details of an analysis at 18 months, if applicable, will be specified in a separate SAP.

The ICH guideline E3 "Structure and Content of Clinical Study Reports" is used as a guide to the writing of the plan.

### 2 STUDY DESIGN AND OBJECTIVES

### 2.1 STUDY OBJECTIVES

The objectives of this study are to evaluate the safety and efficacy of ZimuraTM monotherapy intravitreous administration when administered in subjects with geographic atrophy secondary to dry age-related macular degeneration (AMD).

### 2.1.1 Primary Efficacy Endpoint

[figure not shown]
The primary efficacy endpoint is mean rate of change in GA over 12 months measured by fundus autofluorescence (FAF) at three time points: Baseline, Month 6, and Month 12

[figure not shown]
### 2.1.2 Secondary Efficacy Endpoints

[figure not shown]
Two secondary endpoints are pre-specified:

- The mean change in best corrected visual acuity (Early Treatment Diabetic Retinopathy Study [ETDRS] letters) from Baseline to Month 12
- The mean change in low luminance best corrected visual acuity (ETDRS letters) from Baseline to Month 12

### 2.1.5 Safety Endpoints

The following safety endpoints will be evaluated:

- Adverse events (AEs)
- Serious adverse events (SAEs)
- Vital signs (pulse, systolic and diastolic blood pressure)
- Ophthalmic findings (Intraocular Pressure [IOP], ophthalmic examination, fluorescein angiograms, and FAF)
- Electrocardiogram (ECG) (12-lead)
- Laboratory variables (blood: hematology, renal function, hepatic function, and electrolytes; urinalysis)

### 2.2 STUDY DESIGN AND SAMPLE SIZE

Randomized, Double-Masked, Controlled Trial to Assess the Safety and Efficacy of Intravitreous Administration of Zimura (Anti-C5 Aptamer) in Subjects with Geographic Atrophy Secondary to Dry Age-Related Macular Degeneration.

In Part 1, subjects will be randomized in a 1:1:1 ratio to the following dose groups:

- Zimura 1 mg/eye
- Zimura 2 mg/eye
- Sham

In Part 2, subjects will be randomized in a 1:2:2 ratio to the following dose groups:

- Zimura 2 mg/eye + Sham
- Zimura 4 mg/eye (administered as two injections of Zimura 2 mg/eye)
- Sham + Sham

Subjects will receive monthly intravitreal injections of Zimura and/or Sham for 18 months.

The sample size determination for this study is based on **screening** screening methodology presented in Fleming and Richardson (2004). The power calculations are based on the recently released results from a clinical trial of a complement inhibitor, including the estimated precision of the estimated effects on rate of GA growth over 12 months, and including the plausible effect size for Zimura.

In Part 1, approximately 77 subjects are randomized to Zimura 1 mg vs. Zimura 2 mg vs. Sham control, in a 1:1:1 allocation. In Part 2, approximately 200 subjects are randomized to Zimura 2 mg vs Zimura 4 mg vs Sham control, in a 1:2:2 allocation. A total of approximately 277 subjects are to be randomized.

### 2.3 RANDOMIZATION

[figure not shown]
Subjects will be centrally allocated to one of the three treatment groups stratified by factors known to be of prognostic importance in dry AMD:

- Baseline visual acuity < 50 ETDRS letters (20/100 Snellen equivalent) vs. ≥ 50 ETDRS letters
- Size of Baseline geographic atrophy (< 4 disc areas vs.  $\geq$  4 disc areas)
- Pattern of FAF at the junctional zone of GA (None/focal vs. banded/diffuse)

# **3 GENERAL ANALYSIS DEFINITIONS**

### 3.2 DEFINITION OF POPULATIONS

The analysis and reporting of the data from this study will be performed using the following analysis populations:

### 3.2.1 Intention-To-Treat (ITT) Population

The intention-to-treat population (ITT) will consist of all randomized subjects who received at least one dose of study drug, irrespective of the dose actually received. Subjects will be analyzed in the treatment group assigned at randomization. Subjects will be included in a particular analysis, for a particular population, if relevant data is available for analysis (e.g., the primary analysis will require both Baseline and at least one post-Baseline GA measurement, to calculate a change score).

### **3.2.2 Per-protocol (PP) Population**

The per-protocol population (PP) will consist of all ITT subjects without any significant violation of the protocol. The significant and major protocol violations will be defined prior to database lock in a masked fashion.

### **3.2.3** Safety Population

The safety population will include all subjects who received at least one study drug. In the event that subjects receive a dose that differs from the one assigned according to the randomization schedule, safety analyses will be conducted according to the dose actually received rather than according to the dose assigned by randomization. However, subjects who have ever received an injection of Zimura during this trial will be analyzed in the appropriate Zimura group according to the actual injections received.

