### **7.2 Tonometry**

Tonometry will be performed at all time-points specified in Section 10.2 “Trial Assessments”. On days when two injections are given, the second injection may not be administered until the IOP is  $\leq 21$  mmHg or within 5 mmHg of the pre-injection IOP, at which time the IOP is recorded. After the second injection and also

on days with only one injection, the IOP should be measured and recorded at least 30 minutes after the injection and IOP must be < 30 mmHg before the subject leaves the clinic. For the post-injection tonometry, proper care should be taken to minimize the risk of contamination.

Goldmann applanation tonometry must be performed at Screening and pre-injection on Day 1, Months 6, 12, 18, and Early Withdrawal. Tono-Pen may be used at all other timepoints. Goldmann applanation tonometry must also be used to verify intraocular pressure (IOP) reading of  $\geq 30$  mmHg occurring at any time.

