### 9.1.2 Treatment Regimen and Duration

Subjects randomized to active drug or Sham will receive monthly injections of Zimura™ or Sham for 18 months. Monthly doses should be administered at least 21 days apart.

- Part 1 Subjects:
  - Subjects randomized to the Zimura™ 1 mg/eye treatment arm will receive Zimura™ 1 mg/eye (50 µL) intravitreal injection.
  - Subjects randomized to the Zimura 2 mg/eye treatment arm will receive Zimura™ 2 mg/eye (100 µL) intravitreal injection.

- Subjects randomized to the Sham treatment arm will receive Sham injections.
- Commencing with Amendment C, no new subjects will be enrolled in Part 1 of this trial. Subjects in Part 1 who have received greater than or equal to 18 months of Study Drug treatment will be discontinued from the study after Amendment C.
- Part 2 Subjects:
  - Subjects randomized to the Zimura™ 2 mg/eye treatment arm will receive a Zimura™ 2mg/eye injection (100 µL) and a Sham injection
  - Subjects randomized to the Zimura™ 4 mg/eye treatment arm will receive two injections of Zimura™ 2 mg/eye. The injection volume for subjects randomized to this arm will be of (100 µL) per injection.
  - Subject's randomized to the Sham treatment arm will receive 2 Sham injections.

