#### **11.5 Masking Procedures**

It is the responsibility of the Principal Investigator to ensure that the physician assessing adverse events, the VA examiner, all masked study personnel, and the subject remain masked to the subject's treatment assignment.

For subjects receiving both Zimura™ and Sham injections, the Zimura™ injection must be administered first. To maintain masking, the IRT system will provide instructions as to which kit is to be administered first at each dispensing visit. These instructions are located on the IRT confirmation of drug assignments, which is provided for each dispensing visit. This information must be communicated to the unmasked injector and stored with subject's study documentation.

Within each study drug kit there is a dosing label which indicates the amount of medication to be administered to the subject, based upon the randomized treatment arm of the subject. This dosing label may only be seen by unmasked study personnel.

In the case of a rare emergency where, in the Investigators opinion, unmasking the treatment is necessary to evaluate a further course of action, the Investigator should access the IRT and follow the instructions to initiate unmasking. Every effort should be made to contact the sponsor prior to unmasking a subject. Any unmasking should be reported to the unmasked contact at the sponsor immediately.

In the event of an unmasking, the Investigator will be informed of the subjects randomized treatment assignment. Any unmasking information must be stored separately from the subject's study files in a secure location to ensure the treatment assignment remains masked to other site, CRO and sponsor personnel as required. The IRT system will generate an email notification that does not contain unmasking information, which will be sent to the Investigator and appropriate Sponsor personnel.

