### 4.2 TREATMENT MISALLOCATIONS

For subjects with errors in treatment allocation, the following is described under which treatment groups they will be reported for efficacy and safety analyses:

For example, if subjects were:

- Randomized (regardless of error) but not treated, then they will be excluded for all efficacy and safety analyses. These subjects will be included in the summary of subject dispositions.
- Treated but not randomized, then by definition they will be excluded from the efficacy analyses since randomization is missing, but will be reported under the treatment they actually received for all safety analyses.
- Randomized but were administered the incorrect treatment at any time during the study, then they will be reported under their randomized treatment group for efficacy analyses on ITT population, but will be reported under the treatment they actually received for all safety analyses on SAFETY population (see Section 3.2.3); specifically, this implies that for safety analyses, a patient who ever received Zimura will be included in the applicable Zimura group based on actual injections received.

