### 8 SAFETY EVALUATION

All safety analyses will be performed on the safety population. The analyses will be conducted according to the treatment that they actually received. However, subjects who have ever received an injection of Zimura will be analyzed in the Zimura group. Missing values of safety data will not be imputed and safety summaries will be based on the observed cases.

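### SAP 3.2.3 groups safety subjects by dose received, so on its literal text a 4 mg subject whose second injection is never given can be tabulated under 2 mg

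*SAP*

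**What the plan says.** Three SAP sections govern how subjects are grouped for safety.

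- Section 3.2.3 applies when the dose received differs from the dose assigned: "safety analyses will be conducted according to the dose actually received rather than according to the dose assigned by randomization". It adds that anyone who ever had a Zimura injection "will be analyzed in the appropriate Zimura group according to the actual injections received".
- Section 4.2, on misallocation, covers subjects described as "Randomized but were administered the incorrect treatment at any time during the study". It refers back to 3.2.3 and concludes that "a patient who ever received Zimura will be included in the applicable Zimura group based on actual injections received".
- Section 8 repeats that "subjects who have ever received an injection of Zimura will be analyzed in the Zimura group", without saying which dose group that is.

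The protocol describes the dosing that these rules act on.

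- Section 9.1.2: "Subjects randomized to the Zimura™ 4 mg/eye treatment arm will receive two injections of Zimura™ 2 mg/eye".
- Section 7.2: "the second injection may not be administered until the IOP is" at or below 21 mmHg or within 5 mmHg of its pre-injection value. Section 10.2.3 repeats the condition at each injection visit.
- Section 11.5: "For subjects receiving both Zimura™ and Sham injections, the Zimura™ injection must be administered first".

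Adverse events and serious adverse events are summarised separately for 4 mg, 2 mg and 1 mg (SAP 8.2 and 8.3). IOP categories are tabulated by treatment group (SAP 8.5).

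**The concern.** As-received grouping is normally meant for subjects given the wrong kit, an accident unrelated to how the eye responds. Here the trigger in SAP 3.2.3 is any difference between dose received and dose assigned. In the 4 mg arm such a difference can arise because IOP did not recover after the first injection, or because an acute event stopped the visit. Group membership would then depend on the outcome being tabulated. Protocol 12.1 tightens the link: a clinically significant objective finding that changes trial dosing meets one of the criteria for reporting as an adverse event. The same IOP rise could therefore create the event and move the subject out of the 4 mg column.

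Protocol 11.3 bases the decision on each dose partly on its benefit-to-risk profile. If 4 mg subjects who could not complete the dose are counted under 2 mg, injection-related risk is understated for 4 mg and overstated for 2 mg.

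**Working it through.** **Step 1. Which arms can move.** The table follows a Part 2 visit at which the second injection is never given.

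| Arm | First injection | Second injection | Zimura received if the second is not given |
|---|---|---|---|
| 4 mg | Zimura 2 mg | Zimura 2 mg | 2 mg, differs from assigned |
| 2 mg + Sham | Zimura 2 mg (always first) | Sham | 2 mg, as assigned |
| Sham + Sham | Sham | Sham | none, as assigned |

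Part 1 subjects have one injection per visit and no second injection to withhold. Only the 4 mg arm is exposed, and movement from this cause goes only from 4 mg to 2 mg.

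**Step 2. What the rule does with such a subject.**

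- If the second injection is delayed and given the same day, the dose is 4 mg and nothing changes.
- If a 4 mg subject has the first Day 1 injection only and then stops, the dose received in the whole trial is 2 mg. SAP 3.2.3, read literally, places the subject under 2 mg. SAP 4.2, read alone, does not, because no allocation error occurred.
- If a subject has 4 mg at some visits and 2 mg at others, the SAP does not say whether any visit, most visits or some other rule decides the group. Regrouping is then one permitted reading.

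**Step 3. Arm sizes.** From Protocol 11.3, checked against the allocation ratios in 11.1: 4 mg, 200 × 2/5 = 80. For 2 mg, Part 2 gives 200 × 1/5 = 40 and Part 1 gives 77/3 = 25.7 (stated as 26), so 40 + 26 = 66. The stated figures reproduce.

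**Step 4. How many could move (assumed rates).** The first year as defined in SAP 8.2 holds 12 planned doses, Day 1 to Month 11, or 80 × 12 = 960 dosing visits on 4 mg. Let p be the chance that a second injection is never given at a visit, independent across visits. The expected number of 4 mg subjects with at least one such visit is 80 × (1 − (1 − p)^12).

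| Assumed p | Subjects of 80 |
|---|---|
| 0.25% | 2.4 |
| 0.5% | 4.7 |
| 1% | 9.1 |
| 2% | 17.2 |
| 5% | 36.8 |

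These are the numbers moved only if a single short visit is enough to move a subject. If short visits cluster in the same subjects, fewer are affected. If only subjects who never received a second injection move, the number is smaller still and could be zero.

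**Step 5. Effect on a by-dose table (assumed events).** If k subjects with the event move, the rates become (8 − k)/(80 − k) on 4 mg and (e + k)/(66 + k) on 2 mg, where 8 and e are the assumed event counts as randomised.

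| k | 4 mg | 2 mg, e = 3 | 2 mg, e = 5 |
|---|---|---|---|
| 0 | 8/80 = 10.0% | 3/66 = 4.5% | 5/66 = 7.6% |
| 2 | 6/78 = 7.7% | 5/68 = 7.4% | 7/68 = 10.3% |
| 4 | 4/76 = 5.3% | 7/70 = 10.0% | 9/70 = 12.9% |

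With e = 3, two moved subjects nearly remove the difference and four reverse it. With e = 5, two reverse it. The calculation assumes that every moved subject had the event.

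**The case against.** The strongest reply is that the protocol describes a wait. Section 7.2 holds the second injection until IOP recovers; no visible text says it is then omitted, and no omission rate is given. This stands, and it is why the counts above are illustrations only.

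A second reply is that SAP 4.2 is about errors in treatment allocation and refers to 3.2.3, so the two sections together could be read as covering wrong treatment only. On that reading a 4 mg subject held under the protocol does not move. A reader might infer that a subject stopped after the first Day 1 injection moves on every reading; SAP 4.2 shows that this is too strong. But 3.2.3 carries the broader trigger and defines the population, so the literal reading remains open.

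Third, the first injection is the same 2 mg in 100 µL in both active arms of Part 2, and reporting a one-injection subject under 2 mg is a conventional as-treated choice. That is a fair point about attribution and is the small downside of the fix. It does not justify letting the outcome decide the group.

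Fourth, missing second injections would be traceable: total injections are summarised (SAP 8.1), IOP is shown after each injection (8.5), and listings record onset after the first or second injection (8.2). Traceability does not correct the by-dose tables. Parts of Protocol 9.1.3 and the appendices are blacked out and may contain a rule for a second injection that is not given, but such a dosing rule would not alter the visible SAP grouping rule.

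A reader might also infer, from the grouping rule's lack of a first-year limit, that a kit error after Month 12 could relabel first-year Sham events as Zimura. The documents largely answer this: SAP 1 limits the plan to 1-year data, and Protocol 11.3 locks the database for the 12-month analysis and keeps later information confidential until 18-month follow-up is complete.

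**Conclusion.** The point holds as a defect in wording. On its literal text SAP 3.2.3 can tabulate a 4 mg subject under 2 mg when the second injection is never given; the movement between active arms runs one way and is tied to the safety outcome. The clearest case is a subject who stops after the first Day 1 injection. For subjects with mixed visits, regrouping is possible but not required by the text.

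The size is unknown. It rests on an omission rate the documents do not give and on assumed event counts. With arms of 80 and 66, a few subjects could blur a dose difference. A reader might infer that the order of the two doses will reverse; the documents do not support that, since reversal depends on the event counts assumed. Efficacy is unaffected, because SAP 3.2.1 analyses subjects as randomised.

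**What to change.** In SAP 3.2.3, 4.2 and 8, before database lock:

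1. Restrict as-received regrouping to true kit or allocation errors.
2. State that a subject whose second injection is withheld or not reached stays in the randomised dose group for safety.
3. Report the number of withheld or missed second injections by arm.

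This takes a few sentences and a short table, with no new data. The downside is small: an event in a subject who received only one injection is attributed to the assigned 4 mg regimen, which a footnote or listing can flag. No change to the IOP condition or to any dose is proposed.

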### **3.3 DEFINITION OF SUBGROUPS**

Forest plots will be used to display the primary efficacy results within the following subgroups:

- Size of Baseline geographic atrophy (< 4 disc area vs.  $\geq$  4 disc area)
- Baseline visual acuity < 50 ETDRS letters (20/100 Snellen equivalent) vs. ≥ 50 ETDRS letters

- Pattern of Fundus Auto Fluorescence (FAF) at the junctional zone of GA (None/focal vs. banded/diffuse)
- Subjects from Part 1 vs. Part 2.

### 3.4 DATA HANDLING CONVENTIONS

### 3.4.1 General Conventions

Data will be analyzed using SAS Studio (version 3.6) or R. Descriptive analyses will be performed on Baseline, safety and efficacy data. All tables will be created by treatment arm (Zimura (2 mg), Zimura (4 mg), and Sham) and overall.

- Descriptive statistics will be tabulated as follows:
  - Categorical data will be summarized in contingency tables presenting frequencies and percentages.
  - Continuous data will be summarized using number of non-missing values (n), mean, standard deviation, median, minimum, 1st quartile (Q1), 3rd quartile (Q3), and maximum values.

Listings with individual subjects' data will be provided for all CRF (including derived data) and central laboratory data or other external data. Data collected in the CRF that are *not* present in a table will also be listed (e.g. time and method of tonometry, comments fields, data on Fatal Outcomes page, Unscheduled Visit pages, etc.).

### 3.4.2 Visit Windows

The scheduled visits will be used in the analyses over time.

Missing scheduled follow-up visit will be substituted by an unscheduled or early withdrawal visit occurring within each follow-up visit window, if there is only one unscheduled or early withdrawal visit occurring within the window. If there are multiple unscheduled or early withdrawal visits occurring within the window, the closest one within the visit window will be used. If no unscheduled or early withdrawal visit occurred within the window, the visit will be considered as missing. The *details* are tabulated in **Appendix 1**.

### 3.4.3 Handling Missing Data in Efficacy analyses

Methods that take into account the presence of missing data and that yield valid estimates under the assumption of data missing at random (MAR) will be used. In particular, a Model for Repeated Measures fitted by Restricted Maximum Likelihood method will be used in the primary analysis, where as-observed data will be used with no imputation. Multiple-imputation will be used in sensitivity analyses, whenever necessary, to impute the missing data, as described in Section 7.6.1.

Of note, the proper approach to address missingness is the prevention of missing data. The sponsor will implement aggressive proactive approaches to minimize the number of patients who are not assessed at 12 months.

